## **6.4 Treating the patient**

### **6.4.1 Patient numbering**

Each patient is uniquely identified in the study by a patient number. After the patient has signed the informed consent form, the researcher will telephone the researcher responsible for randomization and provide the requested identifying information for the patient. Then, the researcher responsible for randomization will assign the patient number, which is a 3-digit number (for example, 001, 002, 003, etc.) once assigned to a patient, the patient number will not be reused.

### **6.4.2 Instructions for prescribing and taking the study drug**

The Second Affiliated Hospital of Nanchang University will supply the investigators with all medications sufficient for the course of the study. Patients will be provided with medication packs containing study drug corresponding to their assigned treatment arm and dose level, sufficient to last until the next scheduled visit.

Patients will be instructed to take their morning study drug doses at approximately 08:00 (8 AM) and their evening study drug doses at approximately 19:00 (7 PM). The study medications should be taken with a glass of water with or without food. If the patient misses taking any study drug dose, he/she should take it as soon as possible, unless if it is almost time for the following scheduled dose. In this case, the patient should skip the missed dose and return back to his/her regular study drug administration schedule.

All dosages prescribed and dispensed to the patient and all dose changes during the study must be recorded on the Dosage Administration Record electronic case report form.

The investigator should promote compliance by instructing the patient to take the study drug exactly as prescribed and by stating that compliance is necessary for the patient's safety and the validity of the study. The patient should be instructed to contact the investigator if he/she is unable to take the study drug as prescribed for any reason.

### **6.4.3 Permitted study drug dose adjustments and interruptions**

Every attempt should be made to maintain patients on the target study drug dose level for as long a duration as possible throughout the trial. If, however, in the opinion of the investigator, the patient does not tolerate the target dose of study drug (dose level 3), the investigator should consider whether non-life saving medication (e.g., CCBs, nitrates,  $\alpha$ -blockers) can be reduced to rectify the situation, before considering to reduce the dose of the study drug to the next lower dose level. If adjustment/elimination of

other non-life-saving HF medications is not possible or does not alleviate the side effects of concern, the investigator may down-titrate the dose of the study drug to the next lower level up to complete withdrawal of the study drug. The patient should be re-challenged with the higher dose when the investigator feels it is appropriate to do so per the directions provided below in this section. If needed, the study drug may be stopped completely, but the patient should continue to attend the study visits and be followed until the completion of the study. Ultimately the goal is to keep the patient on the highest study drug dose possible for as long as possible and to follow the patient in the study as long as possible.

Study drug dose level adjustments should mainly be based on overall safety and tolerability with special focus on a) hyperkalemia; b) symptomatic hypotension; and c) clinically significant decrease in eGFR/increase in serum creatinine (see Appendices 2, 3 and 4 for treatment guidelines for hyperkalemia, management of BP, and renal dysfunction, respectively).

### **Adjustment of study drug dose level**

#### **Study drug dose adjustments during the dose titration period**

Once the condition is stable, the patient should increase the titration to the next higher dose level every 2 weeks in an attempt to gradually titrate the patient to the target study drug dose level (dose level 3).

At the investigator's discretion, sacubitril/valsartan 200 mg bid can be down-titrated to sacubitril/valsartan 100 mg bid until such time that investigator believes the patient may be able to tolerate titration back up to sacubitril/valsartan 200 mg bid. If the investigator does not feel that the patient will ultimately be able to tolerate this dose, he/she may withdraw the patient from the study without re-challenge. If the tolerability issues are not alleviated despite down-titration by one dose level, the investigator may lower the study drug dose further to the next lower level for 1 to 4 weeks, up to temporary withdrawal of the study drug. Again, once stable, the patient should be re-challenged with up-titration to the next higher dose level every 1 to 4 weeks in an attempt to bring back the patient gradually to the target study drug dose level (dose level 3).

In some instances, according to the safety and tolerability criteria and the investigator's judgment, dose level 1 or 2 could be maintained if he/she considers that the patient's condition would not allow any further up-titration to the target dose of study medication (level 3). In this case it would be acceptable to maintain the patient at dose level 1 or level 2, whichever is the higher and tolerated dose level by the patient.

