## Glossary of terms

Assessment	A procedure used to generate data required by the study
Enrollment	Point/time of patient entry into the study; the point at which informed consent must be obtained (i.e. prior to starting any of the procedures described in the protocol)
Investigational drug	The study drug whose properties are being tested in the study
Patient number	A number assigned to each patient who enrolls in the study. When combined with the center number, a unique identifier is created for each patient in the study.
Period	A major subdivision of the study timeline; begins and ends with major study milestones such as enrollment, randomization, completion of treatment, etc.
Premature patient withdrawal	Point/time when the patient exits from the study prior to the planned completion of all study drug administration and assessments; at this time all study drug administration is discontinued and no further assessments are planned
Randomization number	A unique identifier assigned to each randomized patient, corresponding to a specific treatment arm assignment
Stop study participation	Point/time at which the patient came in for a final evaluation visit or when study drug was discontinued whichever is later
Study drug	Any drug administered to the patient as part of the required study procedures; includes investigational drug and any control drugs
Study drug discontinuation	Point/time when patient permanently stops taking study drug for any reason; may or may not also be the point/time of premature patient withdrawal
Variable	Information used in the data analysis; derived directly or indirectly from data collected using specified assessments at specified timepoints

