## **6.2 Treatment arms**

Patients who are eligible for randomization at Visit 2 will be assigned to one of the following two treatment arms in a 1:1 ratio:

- Sacubitril/Valsartan dose level 1 or 2
- Enalapril dose level 1 or 2

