#### **6.4.6 Study drug discontinuation and premature patient withdrawal**

The emergence of the following circumstances will require study drug discontinuation:

- Withdrawal of informed consent
- Pregnancy (Section 8.3)
- Investigator thinks that continuation would be detrimental to the patient's well-being
- Suspected occurrence of angioedema during the outpatient dose titration and follow-up period

Study medication may be discontinued at the investigator's discretion if any of the following occurs:

- Any severe suspected drug related adverse event
- Suspected occurrence of angioedema. A patient with any signs or symptoms of clinically significant angioedema should be thoroughly evaluated by the investigator and constitute a reason for interruption of study medication.
- Depending on the serum potassium, blood pressure, or eGFR, patients may need to have their study drug dose or the dose of another concomitant medication reduced or discontinued, or, if appropriate, have potentially contributing agents adjusted. Please refer to Appendices 2, 3, and 4 for treatment guidelines for hyperkalemia, hypotension, or renal dysfunction, respectively.

In the case of study drug discontinuation, the patient should continue to complete all scheduled study visits and procedures. If the patient refuses, he/she should be contacted by telephone in place of protocol-specified visits unless the patient expressly refuses such contacts.

The investigator must also record the discontinuation of the drug administration form of the electronic case report form.

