## **7 Visit schedule and assessments**

All patients, including those who discontinue the study medication before completing the study, should continue attending the scheduled visits as outlined in Table 7-1 until the study ends. At that point all patients will return to the study sites as soon as possible to undergo the end of study visit assessments. If any patient refuses to return for these assessments or is unable to do so, every effort should be made to contact him/her or a knowledgeable informant by telephone to ask if any of the secondary and safety endpoints have occurred at the foreseen visit dates for the remaining duration of the study. Documentation of attempts to contact the patient should be recorded in the patient's record.

All data obtained from the assessments listed in Table 7-1 and described in detail in the subsections below must be supported in the patient's source documentation (e.g., medical charts or patient notes).

Table 7-1 indicates which data remain in source documents only (S), or may be entered directly into the database (D; i.e., these data are considered source documentation and do not require separate source documentation), or are entered into the database from separate source documents (DS). Assessments that generate data for database entry and are recorded on electronic case report forms are listed using the electronic case report form name. Assessments that are transferred to the database electronically (e.g., laboratory data) are listed by test name.

There is a short washout periods (approximately 36 hours for each) during the randomization period to minimize the potential risk of angioedema due to overlapping ACE-NEP inhibition at Visit 2 (Section 7.5.7): after randomization at Visit 2.

For example, if a patient's Visit 2 is on Wednesday, he/she must not take any doses of the enalapril medication after the Tuesday evening dose. The patient will then start to take the first dose of the sacubitril/valsartan medication on Thursday morning.

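### Section 6.4.3 lets the investigator remove a patient from the study, not only from study drug, for expected intolerance of the top dose, against the protocol's own follow-up rule and at the risk of losing week-12 and week-24 primary data

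*Protocol*

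**What the plan says.** Four parts of the protocol bear on a patient who cannot hold the target dose.

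- **Section 6.4.3, dose adjustments during the titration period.** Sacubitril/valsartan 200 mg bid may be lowered to 100 mg bid. If the investigator does not believe that the patient "will ultimately be able to tolerate this dose, he/she may withdraw the patient from the study without re-challenge". This is a permission, not a requirement. The last paragraph of the same subsection covers a patient who cannot go up to level 3: "In this case it would be acceptable to maintain the patient at dose level 1 or level 2".
- **Section 6.4.3, opening paragraph.** Stopping drug does not end participation: "the study drug may be stopped completely, but the patient should continue to attend the study visits and be followed until the completion".
- **Sections 6.4.6 and 7.** "In the case of study drug discontinuation, the patient should continue to complete all scheduled study visits and procedures"; a patient who refuses is to be followed differently: "he/she should be contacted by telephone in place of protocol-specified visits unless the patient expressly refuses such contacts". Section 7 is general: "All patients, including those who discontinue the study medication before completing the study, should continue attending the scheduled visits".
- **Glossary.** Study drug discontinuation and premature patient withdrawal are separate entries. For the latter, "at this time all study drug administration is discontinued and no further assessments are planned".

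Section 10.3.1 sets the primary outcomes as change in NT-proBNP through weeks 4, 12 and 24 and in the echo parameters through weeks 12 and 24. Section 10.1 analyses all randomized patients as assigned.

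**The concern.** A patient who stops study drug altogether must be followed to the end, while a patient who tolerates a lower dose may be taken out of the study. The protocol gives no reason for this difference.

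An investigator who follows the sentence ends data collection for a reason tied to tolerability and to personal judgement. The full analysis set keeps such a patient in the denominator but cannot supply measurements that were never taken, and no later choice of analysis method can do so either. The telephone contact in sections 6.4.6 and 7 would not help with the primary outcomes: it asks about clinical and safety events and cannot yield an echocardiogram or an NT-proBNP value.

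**Working it through.** **1. Is it only loose wording?** The sentence after the permission speaks of temporary withdrawal of the study drug, so the paragraph itself distinguishes leaving the drug from leaving the study. The Glossary does the same. As written, the instruction ends participation. The clause appears again under the heading on restarting study drug; that looks like a duplicated block of text and is not counted as separate evidence.

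**2. When would it act?** Section 6.2 starts patients at "Sacubitril/Valsartan dose level 1 or 2" (enalapril likewise), and section 6.4.3 moves them up every 2 weeks.
- Start at level 2: level 3 first reached at week 2.
- Start at level 1: level 3 first reached at 2 + 2 = week 4.
- Section 4.2.3 asks for every attempt to finish titration within 8 weeks, and 8 < 12.

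This is a target. Section 6.4.3 also allows 1 to 4 weeks at a lower level and 1 to 4 weeks per step back up. For example, level 3 at week 4, then 4 weeks lower and one 4-week step, gives 4 + 4 + 4 = week 12. Withdrawals would mostly come before week 12, but not necessarily all of them.

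**3. What is lost?** A patient withdrawn between week 4 and week 12 loses the week-12 and week-24 values of all four primary variables. One withdrawn before week 4 also loses the week-4 NT-proBNP. For the secondary composite, section 8.2 keeps all SAEs reportable for 30 days after participation stops, and after that only those suspected to be drug-related. Non-serious events are lost from withdrawal on. After 30 days, serious events not suspected to be drug-related are lost too.

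**4. Power.** Inputs from section 10.6: LVEF difference 3 points, SD 6 points, alpha 0.05 (two-sided assumed, since it reproduces the figure), power 80%, 1:1 allocation, 10% loss.
- The plan's figure: a two-sample t-test needs 63.8, so 64 per group. 128 / 0.9 = 142.2, against the stated 142, or 71 per arm. Reproduced.
- Evaluable patients per arm = 71 × (1 − total loss). The loss rates above 10% are assumptions.

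| Total loss, both arms | Evaluable per arm | Power (t-test) |
|---|---|---|
| 10% (planned) | 63.9 | 80.1% |
| 15% | 60.4 | 77.8% |
| 20% | 56.8 | 75.2% |
| 30% | 49.7 | 69.4% |

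If these withdrawals fit inside the planned 10%, power does not change.

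**5. Bias.** Let f be the share withdrawn in an arm, and g the amount by which completers' mean LVEF change exceeds that of withdrawn patients. A complete-case mean is then too high by f × g, and the treatment difference is biased by f₁g₁ − f₂g₂. The protocol gives none of these four quantities. The values below are assumptions that only show how the formula behaves:
- Equal shares and equal gaps: 0.
- 20% against 10%, common gap of 2 to 6 points: 0.10 × 2 = 0.2 to 0.10 × 6 = 0.6 points.
- 10% in each arm, gaps of 6 and 2 points: 0.6 − 0.2 = 0.4 points, with the sign reversed if the gaps are swapped.

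The formula ignores the baseline adjustment in section 10.3.2, which would absorb any part of the gap explained by baseline LVEF. It also assumes a complete-case analysis, which the protocol does not specify.

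**The case against.** The best defence is that the intent is clear. Three other provisions keep patients in follow-up, and section 6.4.3 states the aim of following each patient as long as possible. Section 6.4.6 does not list failure to reach the top dose as a ground for leaving. One permissive sentence stands against all of this and may be a slip for withdrawing study drug. That is plausible, and it makes this an inconsistency more than a deliberate design decision. It does not remove the point: the sentence is an operative instruction, and it is the one that addresses this exact situation.

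A reader might go further and infer any of the following, none of which the documents support.
- *Loss in the sacubitril/valsartan arm only, so a bias in a known direction.* The sentence names that drug alone, but the trial is double-blind with matched dose levels (sections 4 and 6.1). In practice the rule would have to be applied by dose level in both arms.
- *No bias if equal shares withdraw.* As shown above, that also needs the same outcome gap in each arm.
- *An underpowered trial.* Power falls only if these losses come on top of the 10% already allowed, and the protocol gives no rate of dose intolerance.
- *Withdrawal always by week 8.* The 8 weeks are a goal.

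**Conclusion.** The conflict is real and rests on the text alone: the permission in 6.4.3 contradicts the opening of the same section, 6.4.6 and section 7, and sits beside an option to stay on a lower dose. Used as written, it can lose the week-12 and week-24 primary values and later composite events for a reason linked to tolerability.

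The consequence cannot be sized from the protocol. The direction and amount of any bias are unknown and could be zero. Power is unchanged within the planned 10% loss, and about 75% if total loss reached an assumed 20%. The case for correction rests on the fact that the data cannot be recovered and the remedy costs almost nothing, not on a demonstrated bias. Removal under the exclusion criteria or Appendix 4 is a separate matter and is not covered here.

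**What to change.** In the titration paragraph of section 6.4.3, replace the permission to withdraw the patient from the study with wording to this effect: *the investigator may maintain the highest tolerated dose level, or discontinue study drug, without re-challenge; the patient remains in the study and continues all scheduled visits and assessments through week 24 unless consent is withdrawn, with telephone contact as in 6.4.6 if visits are refused.* Name dose level 3 and dose level 2 in place of the sacubitril/valsartan doses, so that the rule reads the same for both arms under blinding. Make the same change where the clause is repeated under the restart heading, or delete the duplicate.

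The cost is one sentence and a change of dose names. The visits and the telephone fallback are already in the protocol, and the sample size of 64 per group and 142 in total stands.

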#### **Study drug restart after temporary treatment interruption**

Study drug should be reintroduced in those who temporarily discontinue it as soon as medically justified in the opinion of the investigator.

Once the investigator considers the patient's condition appropriate for receiving the study drug, the investigator should re-start the patient on the study drug at the most appropriate and allowable dose level (Figure 1) per his/her medical judgment. If

he/she may withdraw the patient from the study without re-challenge. If the tolerability issues are not alleviated despite down-titration by one dose level, the investigator may lower the study drug dose further to the next lower level for 1 to 4 weeks, up to temporary withdrawal of the study drug. Again, once stable, the patient should be rechallenged with up-titration to the next higher dose level every 1 to 4 weeks in an attempt to bring back the patient gradually to the target study drug dose level (dose level 3).

In some instances, according to the safety and tolerability criteria and the investigator's judgment, dose level 1 or 2 could be maintained if he/she considers that the patient's condition would not allow any further up-titration to the target dose of study medication (level 3). In this case it would be acceptable to maintain the patient at dose level 1 or level 2, whichever is the higher and tolerated dose level by the patient.

### **Study drug restart after temporary treatment interruption**

Study drug should be reintroduced in those who temporarily discontinue it as soon as medically justified in the opinion of the investigator.

Once the investigator considers the patient's condition appropriate for receiving the study drug, the investigator should re-start the patient on the study drug at the most appropriate and allowable dose level (Figure 1) per his/her medical judgment. If tolerated based on the safety and tolerability criteria in Appendices 2, 3, and 4, the patient should be up-titrated up to dose level 3 every 1 to 4 weeks, as per the investigator's judgment. Patients re-started on the study drug will retain their original randomization and study identification numbers. Should the patient not tolerate the re-start study drug dose level, he/she may be down-titrated again (if appropriate) or discontinue the study medication again and a new attempt to up-titrate or reintroduce the study drug could be considered by the investigator as soon as medically justified in his/her medical judgment.

Study visits should occur as close as possible to the time points indicated in Table 7-1. The timeframe between the regular visits should be maintained as scheduled, irrespective of the number of unscheduled visits that may be performed in between, according to the visit and time schedule described in Table 7-1.

Any changes in the study drug dose level, including temporary/permanent withdrawal or restart of the study drug, must be recorded on the Dosage Administration Record electronic case report form.

In case of pregnancy discovered during the screening period, the patient will be withdrawn from the study immediately.

In case of pregnancy discovered during the follow-up period, the patient should be instructed to stop taking the study drug immediately.

Study drug intake should be resumed as soon as possible after the completion of the pregnancy and lactation period. Meanwhile, the patient should continue to attend scheduled study visits.

See Section 8.3 for further details on pregnancies and reporting guidelines.

#### **6.4.4 Rescue medication**

Guidance on handling hyperkalemia, hypotension, and renal dysfunction are provided to investigators in Appendices 2, 3, and 4, respectively. Patients may receive other ACEIs and/or ARBs during the study ONLY if the study medication has been discontinued either temporarily or permanently.

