## **4 Study design**

This study is a single-center, prospective, randomized, double-blind, parallel-group, two-arm, short-term trial to compare sacubitril/valsartan 200 mg bid to enalapril 10 mg bid in concentration of NT-proBNP reduction and main cardiac ultrasound parameters improvement in patients with acute anterior STEMI after PCI.

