### **4.2.2 Randomization**

#### **Visit 2 (Randomization Visit)**

Patients who have met all the inclusion criteria and none of the exclusion criteria at the end of the screening period will be randomized to either enalapril or sacubitril/valsartan in a 1:1 ratio. Patients randomized to enalapril continue to receive enalapril, while

patients randomized to sacubitril/valsartan discontinue enalapril to ensure a minimum 36-hour washout period prior to initiation of ARNi therapy. The first dose of sacubitril/valsartan is followed by 6 hours of monitoring for hypotension. After the condition is stable, patients can be discharged from the hospital at any point in time at the discretion of the clinician-investigator. The starting dose during the in-hospital initiation phase is selected using a dose titration algorithm based on systolic blood pressure (SBP) (Figure 1).

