##### **ACEIs and ARBs**

Patients pre-study ACEIs/ARBs will be replaced with the study medications.

The concomitant use of other ACEIs or ARBs is strictly prohibited while the patient is receiving study medication, regardless of study period (Outpatient dose titration and follow-up). If the investigator believes that addition of an ACEI or ARB is necessary, then study drug must be discontinued. If not already treated with an aldosterone antagonist, consideration should be given to adding this therapy rather than an ACEI or ARB.

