### **7.5.7 Angioedema**

Angioedema is a type of abrupt swelling that occurs under the skin and/or mucous membranes and is often localized to the head, neck, throat, and/or tongue, but may occur elsewhere, including the genitalia and intestines. Severe cases may be associated with airway compromise. Although, the mechanism is not fully understood, bradykinin has been implicated as the putative mediator. Therefore, medications that raise the levels of endogenous bradykinin by inhibiting the enzymes responsible for its breakdown, such as ACE, aminopeptidase P, and NEP, may result in this potentially dangerous side effect.

Simultaneous inhibition of multiple breakdown pathways of bradykinin is thought to significantly increase the risk of occurrence of angioedema. Section 4.2.2 details how to avoid the simultaneous inhibition of the ACE and NEP pathways by overlapping exposure to sacubitril/valsartan and enalapril at Visit 2 (randomization). The method outlined in Section 4.2.2 is expected to provide at least 36 hours free of significant simultaneous inhibition of NEP and ACE, thereby minimizing the potential risk of occurrence of angioedema. This 36-hour washout period is expected to present minimal risk to patients.

The procedure for reporting angioedema-like events is outlined in Section 8.5.

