**Serum potassium  $> 5.5$  and  $< 6.0$  mmol/L**

- Confirm potassium concentration in a non-hemolyzed sample
- Consider down-titration or temporarily discontinue study drug according to investigator medical judgment.
- Apply all measures outlined for serum potassium  $> 5.3$  and  $\leq 5.5$  mmol/L
- Repeat serum potassium measurement after 2-3 days
- If serum potassium  $< 5.5$  mmol/L, consider resumption of study drug at lower dose with repeat potassium within 5 days

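### The 36-hour separation between an ACE inhibitor and sacubitril/valsartan is set only for Visit 2; later ACE-inhibitor rescue and study-drug restart carry no minimum interval

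*Protocol*

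**What the plan says.** **The planned switch.** Section 4.2.2 has an explicit rule: "patients randomized to sacubitril/valsartan discontinue enalapril to ensure a minimum 36-hour washout period prior to initiation of ARNi therapy". Section 7 repeats it for Visit 2 with a weekday example. Section 7.5.7 gives the reason, namely that blocking several bradykinin breakdown pathways at once is thought to raise angioedema risk, and relies on the Visit 2 procedure to prevent this: "The method outlined in Section 4.2.2 is expected to provide at least 36 hours free of significant simultaneous inhibition of NEP and ACE".

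**Later switches.** Section 6.4.4 says "Patients may receive other ACEIs and/or ARBs during the study ONLY if the study medication has been discontinued either temporarily or permanently". Section 6.4.3, on restart after interruption, says "Study drug should be reintroduced in those who temporarily discontinue it as soon as medically justified in the opinion of the investigator". Section 6.4.5 adds "The concomitant use of other ACEIs or ARBs is strictly prohibited while the patient is receiving study medication, regardless of study period", and requires study drug to be stopped if an ACE inhibitor or ARB is thought necessary. None of these, and none of Appendices 2 to 4, gives a minimum time between the two drugs.

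**Blinding.** Section 4: "This study is a single-center, prospective, randomized, double-blind, parallel-group, two-arm, short-term trial".

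**Two smaller items.** Section 6.4.6 lists suspected angioedema twice: among the events that require stopping (limited to the outpatient titration and follow-up period) and among those where stopping is at the investigator's discretion (no period given). In Appendix 4 both eGFR-decline triggers measure the fall from a baseline at Visit 5.

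**The concern.** The protocol treats stopping an ACE inhibitor and starting sacubitril/valsartan as hazardous unless 36 hours separate them. That hazard comes from the drugs and not from the visit. If a sacubitril/valsartan patient is interrupted, receives an ACE inhibitor under 6.4.4 and is restarted under 6.4.3, the same switch occurs with no interval stated. The reverse order, from study drug to ACE inhibitor, has none either. An investigator who follows both sections, and does not know the arm, could produce by carry-over the overlap that 7.5.7 warns against.

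At stake is the safety of a subset: patients in the sacubitril/valsartan arm who interrupt and are given an ACE inhibitor. ARBs are outside the concern, since the rationale in 7.5.7 is ACE plus neprilysin inhibition.

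**Working it through.** **Inputs**
- Dose times of about 08:00 and 19:00 (section 6.4.2).
- Minimum interval of 36 h at Visit 2 (section 4.2.2).
- Example in section 7: last enalapril dose Tuesday evening, first sacubitril/valsartan dose Thursday morning.
- Assumption: a rescue ACE inhibitor is taken at the same clock times as study drug. The protocol does not say.

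**Step 1. Reproduce the plan's own interval.** Tuesday 19:00 to Thursday 08:00 = 5 h (to midnight) + 24 h + 8 h = 37 h. This meets the 36 h minimum.

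**Step 2. Shortest slot-to-slot gap that the later text leaves open.**
- Last dose at 08:00, next slot 19:00 the same day: 19 − 8 = 11 h, which is 36 − 11 = 25 h short of the Visit 2 standard.
- Last dose at 19:00, next slot 08:00 the next day: 5 + 8 = 13 h, which is 36 − 13 = 23 h short.

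**Step 3. First slot that meets 36 h if the rule is extended.**

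| Last dose of the first drug | Later slots, hours after that dose | First slot at 36 h or more | Slots skipped |
|---|---|---|---|
| 19:00 | 13, 24, 37 | 37 h | 2 |
| 08:00 | 11, 24, 35, 48 | 48 h | 3 |

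**Step 4. Does another section close the gap?** Section 6.4.5 forbids the two drugs together while study drug is being taken. Once study drug is stopped, that condition is met and 6.4.4 applies at once. Section 4.2.2 shows that the protocol does not regard stopping one drug as enough, since otherwise no washout would be needed at Visit 2. The prohibition therefore does not replace an interval.

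**Step 5. The smaller items.** Table 7-1 lists visits 1, 2, 3a to 3d and 4a to 4e, so there is no Visit 5. Section 10.2 supplies a usable baseline: the last value available before the first randomized dose. In 6.4.6 the mandatory angioedema entry covers the outpatient periods only, so a suspected case in hospital, soon after the switch from enalapril, falls under the discretionary entry.

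**The case against.** The case against giving this much weight has several parts.

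- *It is an omission on a narrow path.* Dose changes are driven mainly by hyperkalemia, symptomatic hypotension and falling eGFR, which are poor reasons to start an ACE inhibitor. Section 6.4.5 prefers an aldosterone antagonist, restart needs medical justification, and staff at this single center already apply the 36 hours at Visit 2. The Drug Instructions mentioned in section 8.1 may also address it, but are not shown. This limits how often the problem would arise. It does not remove it, because the written permissions fall below the protocol's own standard and an unplanned switch has less structure around it than the planned one.
- *The 36 hours is sourced for one direction and one drug.* This stands. The protocol gives it for enalapril to sacubitril/valsartan only. Other ACE inhibitors and the reverse direction are extensions and must be labeled so.
- *Visit 2 already treats the arms differently.* Only sacubitril/valsartan patients stop enalapril there, and 6-hour monitoring is stated only after their first dose. Protecting the blind is therefore a weak reason for a rule in both arms. The better reason is practical: an investigator who does not know the arm cannot apply the interval selectively.
- *In-hospital angioedema is not ignored.* Section 6.4.6 says that signs of clinically significant angioedema are grounds for interrupting study drug, and separately requires stopping whenever continuing would harm the patient. That softens the split between the two lists without removing it.

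A reader might infer that the protocol allows an ACE inhibitor and sacubitril/valsartan together, or directs a switch after 11 hours. It does neither: concomitant use is prohibited and no switch time is prescribed.

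**Conclusion.** The point holds as a gap in the dosing-safety text that should be fixed. The 36-hour separation is written only for Visit 2, while 6.4.4 and 6.4.3 together permit the same switch later with no minimum. Under the assumption of shared dose times, 11 to 13 h is not excluded, against at least 36 h at Visit 2. This is a permitted worst case, and the documents give no frequency.

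A reader might go further and infer a biased efficacy or safety comparison, or unusable renal monitoring. The documents support neither. Nothing shows how many patients would be affected, and the Appendix 4 triggers prompt a search for reversible causes, with absolute creatinine limits that work as written. The Visit 5 reference and the angioedema listing are minor corrections. Sample size, power and analysis do not change.

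**What to change.** 1. In 6.4.3 (restart), 6.4.4 and 6.4.5, require at least 36 hours from the last ACE-inhibitor dose to study-drug restart. This is the protocol's own interval, extended from enalapril to any ACE inhibitor.
2. In the same places, require 36 hours from the last study-drug dose to any ACE inhibitor, and state that this is an extension based on the overlap rationale in 7.5.7.
3. Apply both rules to both arms while the investigator does not know the arm. State that ARBs need no interval.
4. In 6.4.6, keep suspected angioedema only in the mandatory list, and remove the outpatient-period limit there.
5. In both Appendix 4 eGFR triggers, replace the Visit 5 reference with the section 10.2 baseline.

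**Cost.** A wording amendment. The clinical downside is a gap in RAAS blockade of 37 to 48 h at each switch to or from an ACE inhibitor, including in enalapril patients, who do not need the separation. Using an ARB, which 6.4.4 already allows, avoids it.
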